11.4.3. Fasting Lipid Panel

Fasting lipid panel includes total cholesterol, low-density lipoprotein cholesterol (LDL-C), high-density lipoprotein cholesterol (HDL-C), and triglycerides. For subjects with available baseline values, mean values and mean changes from baseline will be presented. The proportion of subjects with clinically meaningful post-baseline increases in lipids will be summarized based on the criteria presented in [Table 5](#) for the dose escalation, dose expansion, combined Phase 1.

Table 5: Changes of Interest in Lipids

Laboratory Test	Parameters for Any Value and the Last Value
LDL Cholesterol	>ULN and >10% increase from BL
LDL-C/HDL-C Ratio	>3.5 and >10% increase from BL

11.4.4. Urinalysis

The results will be listed.

11.4.5. Coagulation Analysis

Coagulation includes the following tests: prothrombin time with international normalized ratio (INR) and partial thromboplastin time. Post baseline and changes from baseline will be analyzed descriptively.

11.4.6. Bone Marrow Blast

Post baseline and changes from baseline will be provided for Bone Marrow Myeloblasts (%). In addition, figures for the mean of Bone Marrow Myeloblasts by visit will be provided for the combined Phase 1, Phase 2, and Phase 1/2 R/R AML.

11.5. Vital Sign Measurements

Unless otherwise specified, all vital sign tables in this section will be produced as described in items 1 to 5 in [Section 5.1](#) for the SAS.

Descriptive statistics for vital signs (except height), both observed values and changes from baseline by scheduled visit, will be summarized.

In addition, a shift table will show the number of subjects with high, normal, low values by treatment group and by parameter at each visit. Normal ranges are defined below (anything lower than the low limit is a low value, anything higher than the upper limit is a high value).

1. Temperature 35-38 °C
2. Systolic blood pressure (SBP) 100-140 mmHg
3. Diastolic blood pressure (DBP) 60-90 mmHg
4. Pulse 60-100 beats per minute (bpm)
5. Respiration 12-20 bpm

A by-subject listing will be presented for each phase of the study.

11.6. Physical Examination

Descriptive statistics for changes in weight from baseline by visit will be summarized in items 1 to 5 in [Section 5.1](#) for the SAS.

Other abnormal physical examination findings will be captured as medical history (screening) and will be summarized as medical history, or will be captured as AEs and will be summarized as AEs.

A by-subject listing will be presented for each phase of the study.

11.7. Electrocardiograms

Electrocardiogram lab data will be summarized as described in items 1 to 5 of [Section 5.1](#).

Electrocardiogram parameters from the central ECG lab include heart rate, PR interval, QRS duration, RR interval, QT, QTc Fridericia value (QTcF) and QTc Bazett value (QTcB). QTcB is not recorded in the CRF page and will be calculated in the following way: $QTcB = QT / \sqrt{RR}$.

Central ECG lab-reported values of ECG parameters and change from baseline values will be summarized at each time point.

Electrocardiogram data for each subject will be provided in a data listing for each phase of the study.

In addition, based on the central ECG lab derived data, the proportion of subjects with maximum post-baseline absolute QTcF and QTcB intervals that fall into following categories will be presented:

1. ≤ 480 ms
2. > 480 to ≤ 500 ms
3. > 500 ms

At maximum post-baseline visits, the proportion of subjects who have an increase from baseline in QTcF and QTcB intervals of the following categories will be presented:

1. ≤ 30 ms
2. > 30 to ≤ 60 ms
3. > 60 ms

Maximum post-baseline absolute value categories and the maximum increase from baseline categories of QTcF will be summarized by baseline QTcF intervals where baseline QTcF intervals are:

1. ≤ 450 ms
2. > 450 to < 470 ms
3. ≥ 470 to < 500 ms
4. ≥ 500 ms

11.8. Left Ventricular Ejection Fraction

LVEF data will be summarized for each visit using the SAS as described in items 1 to 5 of [Section 5.1](#). Change from baseline values will be summarized at each visit.

A by-subject listing will be presented for each phase of the study.

11.9. ECOG Performance Status

Shift tables will be provided for ECOG PS from baseline to post baseline by visit, and from baseline to worst/best/last values across all visits. ECOG data will be summarized in SAS as described in items 1 to 5 of [Section 5.1](#).

A by-subject listing will be presented for each phase of the study.

12. INTERIM ANALYSIS

Formal interim analyses based on the cut-off dates of 15 April 2016 and 14 Oct 2016 for the NDA submission in US and the cut-off date of 01 Sep 2017 for the MAA submission in EU have been undertaken to evaluate the clinical efficacy and safety data of the study treatment for Phase 1 and Phase 2 subjects. In addition, periodically interim reviews of the safety data have been conducted by the Clinical Study Team following completion of each dosing cohort prior to the dose escalation and enrollment in next cohort during Phase 1 dose escalation phase, and every 8 weeks during the Part 1 Expansion phase.

13. CHANGES TO THE STATISTICAL ANALYSES SECTION OF THE PROTOCOL

- The cut-off date of 01 Sep 2017 for the MAA submission was added.
- Use ‘response’ instead of ‘remission’ for CR, PR, CRR, etc.
- Add secondary endpoints of CR/CRi/CR_p rate, CR/CR_h rate, DOCR/CR_h, and TTCR/CR_h.

15. APPENDICES

15.1. Handling of Dates

Dates will be stored as numeric variables in the SAS analysis files and reported in DDMMYY format (ie, the Date9. datetime format in SAS). Dates in the clinical database are classified into the categories of procedure dates, log dates, milestone dates, outcome dates, and special dates.

1. **Procedure Dates** are the dates on which given protocol-specified procedure are performed. They include the dates of laboratory testing, physical examinations, tumor scans, etc. They should be present whenever data for a protocol-specified procedure are present and should only be missing when a procedure are marked as NOT DONE in the database. Procedure dates will not be imputed.
2. **Log Dates** are dates recorded in eCRF data logs. Specifically, they are the start and end dates for AEs and concomitant medications/procedures. They should not be missing unless an event or medication is marked as *ongoing* in the database. Otherwise, incomplete log dates will be imputed according to the rules in Appendix 16.2 (eg, for duration or cycle assignment, etc). However, in listings, log dates will be shown as recorded without imputation.
3. **Milestone Dates** are dates of protocol milestones such as randomization, study drug start date, study drug termination date, study closure date, etc. They should not be missing if the milestone occurs for a subject. They will not be imputed.
4. **Outcome Dates** are dates corresponding to study endpoints such as survival, progression, etc. In most cases they are derived either from a milestone (eg, the survival date is derived from the death date), or a procedure date (eg, the progression date is derived from the date of the tumor scan that was used to determine progression). They may be subject to endpoint-specific censoring rules if the outcome did not occur, but are not otherwise subject to imputation.

Dates recorded in comment fields will not be imputed or reported in any specific format.

15.1.1. Calculation Using Dates

Calculations using dates (eg, subject's age or relative day after the first dose of study drug) will adhere to the following conventions:

1. Study days after the start day of study drug will be calculated as the difference between the date of interest and the first date of dosing of study drug (eg, lenalidomide) plus 1 day. The generalized calculation algorithm for relative day is the following:
 - If TARGET DATE \geq DSTART then STUDY DAY = (TARGET DATE – DSTART) + 1;
 - Else use STUDY DAY = TARGET DATE – DSTART.

- Note that Study Day 1 is the first day of treatment of study drug. Negative study days are reflective of observations obtained during the baseline/screening period. Note: Partial dates for the first study drug are not imputed in general. All effort should be made to avoid incomplete study drug start dates.
- 2. Age (expressed in days) is calculated: $AGE = \text{CONSENT} - \text{DATE of BIRTH} + 1$. In practice, age will be transformed to years by dividing the difference by 365.25 days, then truncating.
- 3. Preference is for using calculated age from clinical database. When not available, calculated age from eCRF or IVRS may be used
- 4. Partial birth date: impute missing day as 15th of the month; impute missing month as July; set missing age for missing year
- 5. Intervals that are presented in weeks will be transformed from days to weeks by using (without truncation) the following conversion formula:
 - $WEEKS = DAYS / 7$
- 6. Intervals that are presented in months will be transformed from days to months by using (without truncation) the following conversion formula:
 - $MONTHS = DAYS / 30.4$

15.2. Date Imputation Guideline

Impute Missing AE/CM/Transfusion Start/Stop Dates:

If the stop date is non-missing and the imputed start date is after the stop date, the start date will be imputed by stop date.

(1) Missing day and month-

- If the year is same as the year of first day on study medication, then the day and month of the start date of study medication will be assigned to the missing fields.
- If the year is prior to the year of first day on study medication, then December 31 will be assigned to the missing fields.
- If the year is after the year of first day on study medication, then January 1 will be assigned to the missing fields.

(2) Missing day only-

- If the month and year are same as the year and month of first day on study medication, then the start date of study medication will be assigned to the missing day.
- If the month and year are before the year and month of first day on study medication, then the last day of the month will be assigned to the missing day.

- If the month and year are after the year and month of first day on study medication, then the first day of the month will be assigned to the missing day.

(3) *Missing day, month, and year-*

- Included as TEAE

Incomplete Stop Date:

If the start date is non-missing and imputed stop date is before the start date then the imputed stop date will be equal to the start date.

(1) *Missing day and month-*

- If the year of the incomplete stop date is the same as the year of the last dose date of study medication, then the day and month of the last dose date will be assigned to the missing fields.
- If the year of the incomplete stop date is prior to the year of the last dose date of study medication, then December 31 will be assigned to the missing fields.
- If the year of the incomplete stop date is after the year of the last dose date of study medication, then January 1 will be assigned to the missing fields.

(2) *Missing day only-*

- If the month and year of the incomplete stop date are the same as the month and year of the last dose date of study medication, then the day of the last dose date will be assigned to the missing day.
- If the month and year of the incomplete stop date are before the month and year of the last dose date of the study medication, then the last day of the month will be assigned to the missing day.
- If the month and year of the incomplete stop date are after the month and year of the last dose date of study medication, then the first day of the month will be assigned to the missing day.

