10.3.1.5. Overall Survival

Overall survival is defined as the time from first dose to the date of death due to any cause. Subjects alive will be censored at the last date known to be alive or a pre-specified data cut-off date, whichever is earlier. The last known alive date is the last non-imputed date of any subject record in the study database. This date may be the last visit date or last contact date that the subject is known to be alive. Subjects who only have a baseline record will be censored at the first dose date.

The OS will be primarily analyzed in the FAS for the Part 1 Expansion, the combined Phase 1, Phase 2, and the combined Phase 1/2 as described in items 2 to 5 of [Section 5.1](#). Due to the limited sample size of each total daily dose group, OS will not be analyzed for Phase 1 dose escalation.

The survival distribution of OS will be estimated using the KM methods. The 25th percentile, median and 75th percentile time with two-sided 95% CI will be provided. KM curves will be provided as well. In addition, KM methods will also be used to estimate the survival probabilities at 3, 6, 9 and 12 months.

Sensitivity analyses for OS will be conducted for the combined Phase 1, Phase 2 and the combined Phase 1/2 where transplanted subjects will be censored at HSCT.

10.3.1.6. 56-Day Transfusion Independence Rate

Subjects who achieved post-baseline 56-day RBC transfusion independence i.e. without RBC transfusion for at least 56 consecutive days post baseline during treatment exposure period will be summarized by baseline RBC transfusion dependence status (Yes vs. No). Subjects with at least one transfusion during the baseline period are considered transfusion dependent at baseline. Baseline period is defined as 28 days before and 28 days after the first dose of treatment for Phase 1, and 56 days before the first dose date for Phase 2.

The post-baseline 56-day Platelet transfusion independence will be analyzed similarly. Subjects who achieved both RBC and Platelet 56-day transfusion independence post baseline during treatment exposure period will be summarized by the status of baseline transfusion dependence i.e. receiving at least one RBC and/or Platelet transfusion during baseline period. Transfusion data will be summarized for the combined Phase 1, Phase 2, and the combined Phase 1/2.

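### SAP 15.2 imputes partial transfusion start dates by the adverse-event rule, which can create or remove a 56-day transfusion independence and misplace a Phase 2 baseline transfusion

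*SAP*

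**What the plan says.** The heading of the rule in SAP 15.2 is "Impute Missing AE/CM/Transfusion Start/Stop Dates", so one rule set covers adverse events, concomitant medications and transfusions.

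For a partial **start** date:
- Day missing, later month than first dose: "If the month and year are after the year and month of first day on study medication, then the first day of the month" is used.
- Day missing, same month as first dose: "then the start date of study medication will be assigned to the missing day".
- Day and month missing, later year: "If the year is after the year of first day on study medication, then January 1 will be assigned to the missing fields".
- Day and month missing, first-dose year: "then the day and month of the start date of study medication will be assigned to the missing fields".
- Earlier month or year than first dose: the last day of that month, or 31 December.
- If a known stop date falls before the imputed start, the start is set to the stop date.

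A partial **stop** date mostly goes the other way. The case that begins "If the month and year of the incomplete stop date are before the month and year of the last dose date of the study medication" takes the last day of the month. An earlier year than the last dose takes 31 December, and the same month or year takes the last-dose date.

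The 56-day transfusion independence rate is a key secondary endpoint (SAP 4.2.1). SAP 10.3.1.6 defines red-cell independence as "without RBC transfusion for at least 56 consecutive days post baseline during treatment exposure period", treats platelets in the same way, and tabulates both by baseline dependence. One transfusion in the baseline period makes a subject dependent. That period is the 56 days before first dose in Phase 2, and 28 days either side of first dose in Phase 1. The section does not say whether the start or the stop date opens a gap, and it plans no sensitivity analysis for partial dates.

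Protocol 12.3 says missing data elements are not imputed. It gives a partial-date rule for adverse-event tabulation only, with the stated aim of being conservative about treatment emergence. SAP section 13 does not list the extension to transfusions as a change.

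**The concern.** Assigning an early date is conservative when the question is whether an adverse event is treatment-emergent. It is not conservative when the question is how long a subject went without a transfusion. Moving a transfusion back adds days to the gap after it and takes the same days from the gap before it. A subject who never had 56 free days can be counted as a success, and a subject who did can be counted as a failure. The same rule can also move a pre-dose transfusion onto Day 1 and so change the baseline group in which the subject is tabulated.

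**Working it through.** The documents give no target or figure for the transfusion-independence rate, so there is nothing of the plan's to reproduce. The check applies the SAP 15.2 rules as date arithmetic.

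**Inputs.** Threshold 56 days (SAP 10.3.1.6). Imputation rules from SAP 15.2. Assumptions: only the day is missing; the month is after the first-dose month and before the last-dose month; the true day d is uniform over the L days of the month; no other transfusion falls in the gap. Free days = next date − previous date − 1.

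**Start or single date.** The transfusion moves from day d to day 1. A true following gap g becomes g + (d − 1). A false success with g ≤ 55 needs d ≥ 57 − g, so for gaps above 56 − L:

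P(false success) = (g − 56 + L) / L

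| True gap g | L = 31 |
|---|---|
| 25 or less | 0 |
| 26 | 1/31 = 3% |
| 35 | 10/31 = 32% |
| 42 | 17/31 = 55% |
| 49 | 24/31 = 77% |
| 55 | 30/31 = 97% |

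For L = 30, gaps of 40, 45 and 50 days give 14/30 = 47%, 19/30 = 63% and 24/30 = 80%. Over all 31 × 56 = 1,736 combinations of d and g from 0 to 55 in a 31-day month, 1 + 2 + … + 30 = 465 (27%) are false successes.

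**Stop date, same grid.** The transfusion moves to the last day of the month, the following gap shrinks, and 0 of 1,736 combinations are false successes.

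**False success, worked.** First dose 10 January 2016; transfusions on 25 February, 29 March (recorded only as March 2016) and 28 April.
- True gaps: 32 and 29 days, so no success.
- Imputed to 1 March: 4 and 57 days, a false success.
- Following gap counted from a stop date imputed to 31 March: 27 days, no success.
- Month also missing: the record moves to 10 January, and the gap from 25 February to 28 April reads 32 + 1 + 29 = 62 days, again false.

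**True success removed.** Transfusions on 20 January, 29 March (day missing) and 20 April 2016. The true gaps are 68 and 21 days, which is a success. Imputed to 1 March they are 68 − 28 = 40 and 21 + 28 = 49 days, and the success is lost.

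**Baseline, Phase 2.** First dose 10 January; the subject's only pre-dose transfusion is on 4 January, with the day missing and no known stop date. It is set to 10 January. The baseline period is the 56 days before that date, so the subject is tabulated as not dependent.

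**Scale.** One misclassified subject is 1/125 = 0.8 percentage points of the planned Phase 2 cohort, and more within a baseline group, whose denominator is smaller.

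**The case against.** The strongest reply is that the same section imputes most stop dates late. If both dates are collected and gaps run from the stop date, the false success disappears, as the grid shows. That stands. It is a full answer only if the plan says gaps run from the stop date, and SAP 10.3.1.6 does not. Protocol 10.4 and 10.8.2 speak only of the dates of the transfusion and the units given, so there may be just one date per transfusion.

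Three further points also stand:
- Errors go both ways, so a net upward bias is not shown.
- Partial dates may be few. Transfusion dates are collected at each response assessment, every 28 days through Cycle 12 in Phase 2, and the 8-week pre-treatment history must be captured. A transfusion with its month unknown should be rare, and other dated transfusions will often break a false gap.
- The baseline error is narrow. A known stop date before first dose prevents it, a date in an earlier month goes to the end of that month, and one other transfusion in the window keeps the subject dependent. In Phase 1 a move to Day 1 stays inside the baseline period.

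The endpoint is descriptive (SAP 10.1), and the primary response-rate criterion is not affected.

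A reader might infer that every partial transfusion date is moved early and that the reported rate is therefore inflated. The documents do not support that: the stop-date and pre-dose rules run late, and the preceding gap shrinks.

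**Conclusion.** The point holds for a single recorded date, or for a start date used to open a gap. There the stated rule can turn a true gap of 26 to 55 days (31-day month, day missing, no other transfusion in the gap) into a false 56-day success, and it can remove a true one. In Phase 2 it misclassifies baseline dependence when the day is missing in the first-dose month, no stop date is known, and that transfusion was the only one in the window.

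The percentages above are conditional on an isolated partial date and a uniform day of the month. They are not estimates of bias in the rate, which cannot be sized without the number of partial dates and may be small. This is a minor point, but the rule gives a wrong answer where it applies and is cheap to replace.

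**What to change.** For the transfusion endpoint, replace the adverse-event start-date rule in SAP 15.2 with these lines:
- A transfusion-free gap opens at the latest possible date of a partially dated transfusion and closes at the earliest possible date of the next one. Both are bounded by the known month or year and by any known start or stop date.
- A partial date that could fall in the baseline period is treated as falling in it.
- SAP section 13 lists the change, because protocol 12.3 limits date imputation to adverse events.

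The first line also settles which date opens and closes a gap. On the grid above it gives 0 of 1,736 false successes, and the worked gap is counted as 27 days (true 29) instead of 57.

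The cost is a few lines of SAP text and no new data. The rule can only understate a gap, so the transfusion-independence rate would be slightly lower. How much lower is unknown, because the number of partial dates is not given. A record with only the year known could block most of that year for one subject.

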15.3. Independent Response Adjudication Committee

For both Phase 1 and Phase 2 of the study, eligibility, treatment decisions, and response to treatment have been determined by the investigators based on modified IWG response criteria. Response will also be assessed by an Independent Response Adjudication Committee (IRAC) based on the modified IWG criteria and CRh definition.

Table 6: Proposed Modified International Working Group Response Criteria for Acute Myeloid Leukemia

Category	Definition
Complete response (CR)*	Bone marrow blasts <5 percent; absence of blasts with Auer rods; absence of extramedullary disease; absolute neutrophil count $>1.0 \times 10^9/L$ (1000/ μ L); platelet count $>100 \times 10^9/L$ (100,000/ μ L); independence of red cell transfusions
CR with incomplete platelet recovery (CRp)	All CR criteria except for residual thrombocytopenia (platelet counts $<100 \times 10^9/L$ [100,000/ μ L])
CR with incomplete recovery (CRi)•	All CR criteria except for residual neutropenia (absolute neutrophil count $<1.0 \times 10^9/L$ [1000/ μ L])
Cytogenetic CR (CRc)◊	Reversion to a normal karyotype at the time of morphologic CR (or CRi) in cases with an abnormal karyotype at the time of diagnosis; based on the evaluation of 20 metaphase cells from bone marrow
Molecular CR (CRm)§	No standard definition; depends on molecular target
Morphologic leukemia-free stateΔ	Bone marrow blasts <5 percent; absence of blasts with Auer rods; absence of extramedullary disease; no hematologic recovery required
Partial response (PR)	Relevant in the setting of Phase I and II clinical trials only; all hematologic criteria of CR; decrease of bone marrow blast percentage to 5 to 25 percent; and decrease of pretreatment bone marrow blast percentage by at least 50 percent
Treatment failure	
Resistant disease (RD)	Failure to achieve CR or CRi (general practice; Phase 2/3 trials), or failure to achieve CR, CRi or PR (Phase 1 trials); only includes patients surviving ≥ 7 days following completion of initial treatment, with evidence of persistent leukemia by blood and/or bone marrow examination
Death in aplasia	Deaths occurring ≥ 7 days following completion of initial treatment while cytopenic; with an aplastic or hypoplastic bone marrow obtained within 7 days of death, without evidence of persistent leukemia
Death from indeterminate cause	Deaths occurring before completion of therapy, or < 7 days following its completion; or deaths occurring ≥ 7 days following completion of initial therapy with no blasts in the blood, but no bone marrow examination available
Relapse (defined only for subjects who have previously attained CR, CRi, CRp or MLFS)	Bone marrow blasts ≥ 5 percent; or reappearance of blasts in the blood; or development of extramedullary disease

Source: ([Cheson, et al. 2003](#))

Footnotes on next page

- * All criteria need to be fulfilled; marrow evaluation should be based on a count of 200 nucleated cells in an aspirate with spicules; if ambiguous, consider repeat exam after 5 to 7 days; flow cytometric evaluation may help to distinguish between persistent leukemia and regenerating normal marrow; a marrow biopsy should be performed in cases of dry tap, or if no spicules are obtained; no minimum duration of response required.
- The criterion of CRi is of value in protocols using intensified induction or double induction strategies, in which hematologic recovery is not awaited, but intensive therapy will be continued. In such protocols, CR may even not be achieved in the course of the entire treatment plan. In these instances, the overall response rate should include CR and CRi patients. Some patients may not achieve complete hematologic recovery upon longer observation times.
- Δ This category may be useful in the clinical development of novel agents within Phase I clinical trials, in which a transient morphologic leukemia-free state may be achieved at the time of early response assessment.
- ◇ Four studies showed that failure to convert to a normal karyotype at the time of CR predicts inferior outcome.
- § As an example, in core-binding factor AML low-level polymerase chain reaction-positivity can be detected in patients even in long-term response. Normalizing to 104 copies of ABL1 in accordance with standardized criteria, transcript levels below 10 to 12 copies appear to be predictive for long-term response.
- ¥ A repeat marrow should be performed to confirm relapse with 2 consecutive assessments separated by at least 1 month. Appearance of new dysplastic changes should be closely monitored for emerging relapse. In a patient who has been recently treated, dysplasia or a transient increase in blasts may reflect a chemotherapy effect and recovery of hematopoiesis. Cytogenetics should be tested to distinguish true relapse from therapy-related MDS/AML.

Table 7: Criteria for Stable Disease and Progressive Disease for Acute Myelogenous Leukemia

Category	Response Criteria
Stable disease	Failure to achieve a response and not meeting the criteria for disease progression
Disease progression	
Progression should be confirmed by 2 consecutive assessments separated by at least 1 month.
 
Development of new biopsy-confirmed extramedullary disease since last disease evaluation.
 
The date of progressive disease is defined as the first date of progression.
 
Progression is defined as the following:
 
For patients with 5 to 67% bone marrow blasts at nadir:
 
 - A >50% increase in bone marrow blast count percentage from the nadir and that is $\geq 20\%$. 
For patients with $\geq 67\%$ bone marrow blasts at nadir:
 
 - A doubling of the nadir absolute peripheral blood blast count and the final absolute peripheral blood blast count is $>10 \times 10^9/L$.

Table 8: Proposed Modified International Working Group Response Criteria for Altering Natural History of MDS

Category	Response criteria (Response must last at least 4 weeks)
Complete response	Bone marrow: $\leq 5\%$ myeloblasts with normal maturation of all cell lines* Persistent dysplasia will be noted* † Peripheral blood ‡ Hgb ≥ 11 g/dL Platelets $\geq 100 \times 10^9/L$ Neutrophils $\geq 1.0 \times 10^9/L$ † Blasts = 0%
Partial response	All CR criteria if abnormal before treatment except: Bone marrow blasts decreased by $\geq 50\%$ over pretreatment but still $> 5\%$ Cellularity and morphology not relevant
Marrow CR †	Bone marrow: $\leq 5\%$ myeloblasts and decrease by $\geq 50\%$ over pretreatment † Peripheral blood: if HI responses, they will be noted in addition to marrow CR †
Stable disease	Failure to achieve at least PR, but no evidence of progression for > 8 wks
Failure	Death during treatment or disease progression characterized by worsening of cytopenias, increase in percentage of bone marrow blasts, or progression to a more advanced MDS FAB subtype than pretreatment
Relapse after CR or PR	At least 1 of the following: Return to pretreatment bone marrow blast percentage Decrement of $\geq 50\%$ from maximum response/response levels in granulocytes or platelets Reduction in Hgb concentration by ≥ 1.5 g/dL or transfusion dependence
Cytogenetic response	Complete: Disappearance of the chromosomal abnormality without appearance of new ones Partial: At least 50% reduction of the chromosomal abnormality

Disease progression	For patients with: Less than 5% blasts: $\geq 50\%$ increase in blasts to $> 5\%$ blasts 5%-10% blasts: $\geq 50\%$ increase to $> 10\%$ blasts 10%-20% blasts: $\geq 50\%$ increase to $> 20\%$ blasts 20%-30% blasts: $\geq 50\%$ increase to $> 30\%$ blasts Any of the following: At least 50% decrement from maximum response/response in granulocytes or platelets Reduction in Hgb by ≥ 2 g/dL Transfusion dependence
---------------------	---

Source: ([Cheson, et al. 2006](#))

AML = acute myeloid leukemia; CR = complete response; DFS = disease-free survival; FAB = French-American-British; Hgb = hemoglobin; HI = hematologic improvement; MDS = myelodysplastic syndromes; PFS = progression-free survival; PR = partial response.

Note: Deletions to International Working Group (IWG) response criteria are not shown.

Note: To convert hemoglobin from g/L to g/dL, divide g/L by 10.

* Dysplastic changes should consider the normal range of dysplastic changes (modification).

† Modification to IWG response criteria ([Cheson, et al. 2003](#))

‡ In some circumstances, protocol therapy may require the initiation of further treatment (eg, consolidation, maintenance) before the 4-week period. Such subjects can be included in the response category into which they fit at the time the therapy is started. Transient cytopenias during repeated chemotherapy courses should not be considered as interrupting durability of response, as long as they recover to the improved counts of the previous course.

